#### 4.4 Multiplicity Strategy

A total of six hypothesis tests will be conducted to address the primary and secondary objectives of the study. All type-I error rates in the following figure are I-sided.

Figure .4-1 Multiple Testing Strategy

#### 4.5 Handling of Missing Data

All data obtained in evaluable subjects will be used in the analysis. No imputation for missing data is planned in the analyses.

#### 4.6 Subgroup Analyses and Effect of Baseline Factors

Subgroup analyses of the primary endpoint will be conducted to assess the consistency of treatment effect across various subgroups.

The consistency of the treatment effect for binocular UCIVA, binocular UCDVA and binocular UCNVA will be assessed descriptively using summary statistics by category of the following subgroup factors:

- Age category (<65 vs. 65 years)
- Sex (Female, Male)

## **4.7 Interim Analysis for Effectiveness**

An interim analysis will be performed when all subjects complete Visit 3A (20-40 days post 2nd eye implantation) in order to support the study publication plan of the test articles for near, intermediate and distance visual acuity, contrast sensitivity, defocus curves and adverse events.

## **5 Safety Analysis Strategy**

### **5.1 Safety Assessments**

The safety assessments are:

- Adverse events (AEs) including secondary surgical intervention (SSI)
- Device deficiencies (DD)
- Surgical problems
- Intraocular pressure (IOP)
- Slit lamp examination
- IOL observations
- IOL position change
- Subjective posterior capsule opacification (PCO)
- Posterior capsulotomy
- Fundus visualization
- Dilated fundus examination

### **5.2 Safety Hypotheses**

There are no formal safety hypotheses in this study. The focus of the safety analysis will be a comprehensive descriptive assessment of safety endpoints listed in Section 5.1.

## **5.3 Statistical Methods for Safety Analyses**

Except otherwise stated, the analysis set for all safety analyses is the safety analysis set as defined in Section 2.2. Baseline will be defined as the last measurement prior to exposure to investigational product, except otherwise stated.

### **5.3.1 Adverse Events**

All information obtained on AEs will be displayed by treatment and subject.

The number and percentage of all ocular adverse events, including secondary surgical interventions (SSIs) for either eye, will be tabulated by preferred term with a breakdown by treatment, separately for first and second eyes. An eye with multiple ocular AEs of the same preferred term is only counted once toward the total of this preferred term.

The number and percentage of all adverse events will also be tabulated with a breakdown by treatment, separately for first and second implanted eyes.

Adverse events will be summarized in the following tables:

1. All Adverse Events (Serious and Non-Serious Combined)
  - a. Ocular
  - b. Non-Ocular
2. All Adverse Device Effects
  - a. Ocular
  - b. Non-Ocular
3. All Serious Adverse Events (including Serious Adverse Device Effects)
  - a. Ocular
  - b. Non-Ocular
4. Subject Listings
  - a. Non-Serious Ocular
  - b. Non-Serious Non-Ocular
  - c. Serious Ocular
  - d. Serious Non-Ocular

### 5.3.2 Device Deficiencies

The number and percentage of all device deficiencies will be tabulated with a breakdown by treatment, separately for first and second implanted eyes. A listing of all device deficiencies, as recorded on the Device Deficiency Form, will also be provided.

### 5.3.3 Surgical Problems

Descriptive statistics (number and percentages) on eyes with surgical problems will be presented, separately for first and second implanted eyes. In addition, a listing of subjects with surgical problems will be provided. The listing will include the following variables: investigator, subject, age, sex, race, ethnicity, treatment, eye and description of surgical problem.

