9.5 Risk Benefit Assessment

9.5.1 Known and Potential Risks

Complications may occur on the surgery day or throughout the postoperative period. As with any type of intraocular surgery, there is a possibility of complications due to anesthesia, drug reactions, and surgical problems. The surgical procedure can exacerbate a pre-existing ocular condition. Possible problems during surgery include corneal endothelial touch, detached Descemet's membrane, iris damage, iris prolapse, iris trauma, iris incarceration, zonular rupture, vitreous loss, capsulorhexis tear, capsular rupture, uncontrollable intraocular pressure, hyphema, and retinal damage. An IOP increase may occur from the surgical procedure, residual viscoelastic in the eye, or a steroid response to postoperative medications.

Additionally, potential postoperative adverse events include but are not limited to corneal stromal edema, cystoid macular edema, endophthalmitis, hypopyon, iritis, lens dislocation, membrane formation on the IOL, pupillary block, retinal detachment, cyclitic membrane, transient or persistent glaucoma, retinal tear, vitritis, iris touch, pupil ovalization, posterior synechiae, ocular inflammation, ocular discomfort or pain, inflammation, decreased vision, decreased contrast sensitivity, decreased color perception, visual disturbances, and corneal endothelial cell loss.

An IOL replacement or explantation may be appropriate in some cases of residual refractive error, ocular infection, subject dissatisfaction, or visual disturbances (eg, glare, halos, starbursts, hazy vision, blurred vision, double vision, visual distortions, and color distortions, etc.). Alternatively, spectacles or contact lenses may be prescribed to resolve residual refractive error. Other secondary surgical interventions include, but are not limited to: IOL repositioning, refractive laser treatment, paracentesis, vitreous aspirations, iridectomy or laser iridotomy for pupillary block, wound leak repair, and retinal detachment repair.

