10.3 Exclusion Criteria During Surgery

Below is a list of criteria that when occurring prior to IOL implantation prevent the study lens from being implanted. This is true for both eyes.

19. Any other additional procedures during the phacoemulsification and IOL implant due to intraoperative complications that require further intervention (including but not limited to posterior capture rupture, vitreous loss, zonular dehiscence that may make the IOL implant less stable, etc.)
20. Uncontrolled intraocular pressure

21. Significant anterior chamber bleeding
22. Excessive iris mobility
23. Mechanical or surgical manipulation required to enlarge the pupil prior to or at IOL implantation (pupil size must be at least 4.5 mm or larger just prior to implantation)
24. Capsulorhexis tears or any areas of “can-opener” capsulotomy
25. Unrecognized (pre-existing but discovered during surgery) ocular conditions or complications in which the IOL stability could be compromised, including zonular weakness
26. Zonular or Capsule rupture
27. Intended IOL haptic placement other than bag-bag

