12.1.2 Operative Visit (Visit 00/00A)

Visit 00: Day 0, Monocular 1st Eye

Visit 00A: 2-21 Days Post 1st Eye Implantation, Monocular 2nd Eye

Below is a list of study procedures to be undertaken at Visit 00 and Visit 00A. It is recommended that procedures are performed in the order described below unless otherwise stated. Activities involving multiple delegated staff members may be performed in parallel. All assessments must be documented in source documentation and case report forms (if applicable).

Note: the Visit 00A window may overlap with other study visit windows (eg, Visit 1, Visit 2). In this case, both visits may be conducted on the same day at the discretion of the Investigator.

1. In preparation for the operative visit, randomize the subject. Randomization should be performed within 10 business days of Visit 00. It is recommended that subjects are contacted prior to randomization to 1) confirm willingness to continue trial participation, and 2) confirm scheduled surgical date and time.
2. Prior to treatment, review inclusion/exclusion criteria and ensure the subject has been properly consented for participation in the trial.
3. Document any changes to ocular and non-ocular concomitant medications.
4. Record operative eye.
5. Prepare subject for surgery in accordance to site specific operating procedures.
[Operative Eye Only, Monocular]
6. Perform surgery and implantation with the randomized IOL.
[Operative Eye Only, Monocular]
7. Record any surgical problems, complications, or other procedures that occur during surgery. Other procedures include those performed outside of routine cataract surgery.
Note: Other planned procedures at the time of surgery are exclusionary.
[Operative Eye Only, Monocular]
8. Record the lens information that is located on the IOL sticker. Both successful and aborted (if applicable) test article information should be recorded.
[Operative Eye Only, Monocular]
9. Record any adverse events including SSIs.
Note: Serious adverse events (SAEs) including SSIs must be entered into EDC within 24 hours of the Investigator's knowledge. Refer to Section 13 for further detail.
10. Record any device deficiencies. Refer to Section 13 for further detail.

12.1.3 1-Day Postoperative Visit (Visit 1/1A)

Visit 1: 1-2 Days Post 1st Eye Implantation, Monocular 1st Eye

Visit 1A: 1-2 Days Post 2nd Eye Implantation, Monocular 2nd Eye

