## **2.2 Safety Analysis Set**

All eyes with attempted test or control article implantation (successful or aborted after contact with the eye) will be considered evaluable for the Safety Set (SS).

The SS will be used for analysis of safety endpoints.

Safety analyses will be conducted using the SS on a treatment-emergent basis. For treatment-emergent safety analyses, eyes will be categorized under the actual test or control article implanted (or attempted to implant).

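### Surgical problems that stop implantation before the lens touches the eye are recorded but fall outside the Safety Set, so the planned table under-counts them

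*SAP*

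**What the plan says.** Surgical problems are a named safety assessment in the Protocol synopsis and in SAP 5.1. Protocol 12.1.2 collects them at both operations, without any condition on lens contact: "Record any surgical problems, complications, or other procedures that occur during surgery".

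SAP 5.3.3 plans two outputs. The table is described as "Descriptive statistics (number and percentages) on eyes with surgical problems will be presented, separately for first and second implanted eyes". The listing follows: "In addition, a listing of subjects with surgical problems will be provided". Neither sentence names an analysis set, so the general rule of SAP 5.3 governs: "Except otherwise stated, the analysis set for all safety analyses is the safety analysis set as defined in Section 2.2".

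SAP 2.2 admits to that set "All eyes with attempted test or control article implantation (successful or aborted after contact with the eye"; Protocol 15.2 has the same definition. Eyes are then classed by the lens actually implanted or attempted.

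Protocol 10.3 introduces its intraoperative criteria, for both eyes, with: "Below is a list of criteria that when occurring prior to IOL implantation prevent the study lens from being implanted". They include capsulorhexis tears, zonular or capsule rupture, uncontrolled intraocular pressure, significant anterior chamber bleeding, and complications needing further intervention. Vitreous loss appears as an example of the last. Protocol 9.5.1 names closely matching events among the possible problems during surgery: "zonular rupture, vitreous loss, capsulorhexis tear, capsular rupture, uncontrollable intraocular pressure, hyphema, and retinal damage".

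**The concern.** Whether an eye enters the surgical-problems table depends partly on the outcome that the table counts. A capsule rupture before the lens is introduced leads to no study lens, hence no lens contact, hence no place in the Safety Set. The rupture is in the case report form but in neither the numerator nor the denominator.

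A reader will take this table as the trial's operative complication rate among randomised subjects. As written, it can show fewer capsule or zonular ruptures than were recorded, and possibly none.

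The second eye is the most awkward case. The subject may already carry a study lens in the first eye and then have a complication in the fellow eye that stops implantation. That second eye is outside the Safety Set. The subject is also outside the all-implanted set, which requires bilateral implantation. Because the Safety Set default also governs SAP 5.3.1, ocular adverse events in the unimplanted eye have the same gap.

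**Working it through.** The plan states no rate of surgical problems, so there is no figure to reproduce. The check is mainly one of definitions.

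**Tracing an eye through the rules**

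1. The subject is randomised within 10 business days of the first surgery (Protocol 12.1.2), so every operated eye has a known assignment.
2. A criterion in Protocol 10.3 is met before implantation. The study lens is not implanted.
3. The problem is recorded (Protocol 12.1.2).
4. If the lens never touched the eye, the eye is neither a success nor abandoned after contact, so it is not in the Safety Set (SAP 2.2).
5. SAP 5.3.3 states no exception to the SAP 5.3 default, and its reference to implanted eyes points the same way. The eye is not in the table.
6. If the same event happens at or after lens contact, step 4 goes the other way and the eye is counted, even if implantation is then abandoned.

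The listing requires a treatment for each entry. SAP 2.2 assigns treatment by the lens implanted or attempted, so an eye that no lens touched has no defined treatment column.

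**Illustration of size**

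Both inputs are assumptions, since the documents give neither: r is the true rate of these events per operated eye, and f is the share occurring before lens contact. With N operated eyes:

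- true rate = r
- table rate = N·r·(1 − f) / (N − N·r·f) = r(1 − f) / (1 − r·f), so N cancels

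Example: r = 2%, f = 50% gives 0.02 × 0.5 / (1 − 0.01) = 0.0100 / 0.99 = 1.01%.

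| True rate r | Table rate, f = 50% | f = 75% | f = 100% |
|---|---|---|---|
| 1% | 0.50% | 0.25% | 0% |
| 2% | 1.01% | 0.51% | 0% |
| 4% | 2.04% | 1.03% | 0% |

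For counts, take 320 operated eyes as a round base and compute 320·r·f. At f = 50% the eyes omitted are 1.6, 3.2 and 6.4 for r = 1%, 2% and 4%. At f = 100% they are 3.2, 6.4 and 12.8.

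The planned 160 subjects × 2 = 320 are implanted eyes, and omitted eyes come on top of them. The correction is small. For r = 2% and f = 50%, operated eyes are about 320 / 0.99 = 323.2, and the omitted number is still about 3.2.

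**The case against.** **The set definition is a coherent choice.** The safety analyses are built on device exposure: treatment-emergent, by actual lens, with baseline taken before exposure to the product. Surgical problems are not among the listed safety endpoints in Protocol 8.4.2; Protocol 15.7 places them with the other safety assessments. SAP 5.2 states that there is no safety hypothesis. This stands. It limits the point to completeness of reporting and argues against replacing the Safety Set, which would also conflict with the as-implanted rule in Protocol 15.1 and SAP 2.2. It does not put the missing eyes back into the table.

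**Other outputs cover part of it.** SAP section 3 plans a listing of subjects excluded from key analysis sets, with reasons. It works by subject, gives no rate, and can miss an excluded second eye whose fellow eye is in the set. The SAP 5.3.3 listing is of subjects while the Safety Set is of eyes, so a second-eye problem might still be listed. The loss from the listing is therefore clear only for first eyes.

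**Stronger readings that the documents do not support:**

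- *That these harms vanish from the table as a class.* Only events before lens contact are lost.
- *That the gravest harms are lost and mainly milder ones remain.* Protocol 9.5.1 does not rank its risks. Retinal damage and iris damage, for instance, are listed there but not named in 10.3.
- *That a zero in the table would appear to exclude a true rate of 2% to 3%.* With zero events in n eyes the one-sided 95% upper limit is 1 − 0.05^(1/n). Pooling both eyes in an arm (n = 160) gives 1.85%, but the planned tables are separate for first and second eyes. With n = 80 the limit is 3.68%, which excludes neither rate. No interval is planned anyway.
- *That the gap between about 180 screened and about 160 bilaterally implanted measures these events.* It covers every reason for not reaching bilateral implantation.
- *That the loss differs by arm because the lenses differ in design.* A lens cannot, by contact, cause an event that precedes contact, and 10.3 sets one rule for both lenses. The masking text covers the subject, the observer and sponsor personnel but does not mention the surgeon, so a difference in the decision to implant is conceivable. Nothing in the documents shows one.

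**Conclusion.** The gap is real and follows from the definitions alone. Surgical problems that stop implantation before lens contact are recorded but left out of the planned table and, at least for first eyes, its listing. The result is an under-count of these events.

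Its size cannot be stated from the documents. Under the assumed values, the table shows about half the true rate if half the events precede contact, about a quarter if three quarters do, and none if all do. In eyes, that means low single figures up to about 13 across the trial for assumed rates of 1% to 4%.

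The effectiveness conclusions are untouched, and no bias between arms is demonstrated. Severity is minor to moderate.

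**What to change.** Keep the Safety Set table in SAP 5.3.3 as planned, and add one supplementary table and listing of surgical problems:

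- **Population:** all eyes in which study surgery was started after randomisation, whether or not the study lens touched the eye. Operated eyes are the denominator.
- **Layout:** by randomised lens, and separately for first and second eyes. The randomised lens supplies the treatment column that an untouched eye otherwise lacks.
- **Timing:** events before lens contact apart from those at or after contact.
- **Reason:** the Protocol 10.3 criterion wherever the study lens was not implanted.

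In SAP 5.3.1, list ocular adverse events in those unimplanted eyes beside the Safety Set tables. Lens-dependent outputs (IOL observations, IOL position, posterior capsule opacification) stay on the Safety Set, and no clinical rule changes.

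The cost is SAP wording, one table and added listings, using surgical problems already recorded at Visits 00 and 00A and adverse events collected from consent. Before programming, confirm that the case report form allows timing relative to lens contact to be derived. The reported complication rate may be slightly higher, partly from surgery rather than the lens; the timing split makes that visible.

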### 5.3.4 Intraocular Pressure

Intraocular pressure (IOP) measurements will be recorded in mmHg and rounded to the nearest whole mmHg.

All analyses will be presented by eye (first eye versus second eye).

Descriptive summaries (N, mean, median, standard deviation, standard error, minimum and maximum) of observed values and change from baseline values will be presented at each study visit by treatment, separately for first and second implanted eyes. A plot of mean change in IOP by study visit and by treatment with error bars representing +/- 1 standard error will be presented, separately for first and second implanted eye. The x-axis will be study visit and the y-axis will be the change in IOP from baseline.

A summary table with number and percentages of eyes in each category of IOP change from baseline to last on-treatment IOP assessment and to any visit by implanted eye will be presented according to the following categories: >30 mmHg increase, 21 to 30 mmHg increase, 11 to 20 mmHg increase, 6 to 10 mmHg increase, -5 mmHg decrease to 5 mmHg increase, 6 to 10 mmHg decrease, 11 to 20 mmHg decrease, 21 to 30 mmHg decrease, and >30 mmHg decrease, separately for first and second implanted eyes. For change to any visit, an eye will be counted only in the category that represents maximum change from baseline across all post-baseline assessments.

A listing will be provided which presents all eyes with an increase or decrease in IOP of more than 10 mmHg at any visit compared to the same eye at baseline. The listing will include the following variables: investigator, subject, age, sex, race, ethnicity, treatment, visit, eye, baseline value, value at the visit and a change from baseline value.

### **5.3.5 Slit Lamp Examination**

For each slit-lamp parameter, number and percentages of eyes that experience abnormality at any post-operative visit will be presented, separately for first and second implanted eyes.

A listing will be provided which presents all eyes with an abnormality in any slit-lamp parameter at any post-operative visit. The listing will include all slit-lamp data from all visits with the following variables: treatment, investigator, subject, age, sex, race, ethnicity, visit, eye, parameter, baseline value, and value at the visit.

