12.1.1 Preoperative Visit (Visit 0)

Visit 0: -60 to 0 Days Prior to Visit 00, Binocular Visit

Below is a list of study procedures to be undertaken at Visit 0. It is recommended that procedures are performed in the order described below unless otherwise stated. All assessments must be documented in source documentation and case report forms (if applicable).

Data from the Investigator's previous routine clinical evaluation (eg, slit lamp exam) may be used, if the data 1) meet the requirements of this protocol and MOP, and 2) were collected within the -60 to 0 day preoperative time period.

1. Review non-study specific inclusion/exclusion criteria (eg, age, previous ocular history) to ensure that a potential subject meets all qualifications for participation in the study.
2. For a potential subject meeting all entry criteria via pre-screening, invite him/her to participate in the study, and carry out the informed consent process if he/she is interested. Refer to Section 16.2 Informed Consent Procedures.
Note: Subjects must formally consent to the trial prior to any study specific testing.
3. Document demographics, ocular and non-ocular medical history, ocular and non-ocular concomitant medications and pregnancy status (where applicable).
4. Perform a urine pregnancy test, IF the subject is a woman of childbearing potential.
5. [REDACTED]
6. [REDACTED]

7. Document the target residual refractive error based the IOL calculation power. [REDACTED]
[Both Eyes, Bilateral]
8. [REDACTED]
9. [REDACTED]
10. Conduct slit lamp examination.
[Both Eyes, Bilateral]
11. Conduct dilated fundus examination.
[Both Eyes, Bilateral]
12. Perform tonometry to measure IOP.
[Both Eyes, Bilateral]
13. Record any AEs. Refer to Section 13 for further detail.
14. Evaluate subject against all entry criteria. If subject fails criteria screen fail the subject.
15. [REDACTED]
16. Proceed with scheduling surgery.

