Any adverse event that does not meet seriousness criteria described above.

Adverse Device Effect (ADE)

Adverse event related to the use of a test article or control article. Note: This definition includes adverse events resulting from insufficient or inadequate instructions for use, deployment, implantation, installation, or operation; any malfunction; and use error or intentional misuse of the test article or control article.

Serious Adverse Device Effect

A serious adverse device effect (SADE) is an ADE that has resulted in any of the consequences characteristic of a SAE.

Serious Public Health Threat

Any event type which results in imminent risk of death, serious deterioration in state of health, or serious illness that requires prompt remedial action. This would include: Events that are of significant and unexpected nature such that they become alarming as a potential public health hazard, eg, human immunodeficiency virus (HIV) or Creutzfeldt-Jacob Disease (CJD).

Figure. 13-1 Categorization of All Adverse Events

[figure not shown]
[figure not shown]

Figure. 13-2 Categorization of All Serious Adverse Events

Specific Events Relevant to this Protocol

In addition to reporting all AEs (serious and non-serious) meeting the definitions, the Investigator must report any occurrence of the following as an SAE:

Cumulative Serious Adverse Events

- Cystoid macular edema
- Hypopyon
- Endophthalmitis
- Lens dislocation
- Pupillary block
- Retinal detachment
- Secondary surgical intervention (excluding posterior capsulotomy)

Persistent Serious Adverse Events

- Corneal stromal edema
- Cystoid macular edema
- Iritis
- Raised IOP requiring treatment

This list is consistent with the categories provided in EN ISO 11979-7:2014. A persistent AE is an AE that is present at the conclusion of a clinical investigation per EN ISO 11979-1:2012. Any other potentially sight-threatening event may also be considered serious based on the judgment of the Investigator and should be reported appropriately as delineated in Section 13.2.

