### **5.3.11 Dilated Fundus Examination**

For each dilated fundus parameter, number and percentages of eyes that experience abnormality at any post-operative visit will be presented, separately for first and second implanted eyes.

A listing will be provided which presents all eyes with abnormality in any fundus parameter at any post-operative visit. The listing will include the following variables: investigator, subject, age, sex, race, ethnicity, treatment, visit, eye, baseline value and value at the visit.

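### The slit-lamp and dilated-fundus summary tables (SAP 5.3.5 and 5.3.11) count postoperative abnormalities without reference to the same eye's baseline, so the rate of new findings per lens cannot be read from them

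*SAP*

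**What the plan says.** SAP 5.3.5 (Slit Lamp Examination) states that for each parameter "number and percentages of eyes that experience abnormality at any post-operative visit will be presented", separately for first and second eyes. SAP 5.3.11 (Dilated Fundus Examination) has the same rule: "For each dilated fundus parameter, number and percentages of eyes that experience abnormality at any post-operative visit will be presented". Neither sentence sets a baseline condition, gives a count by visit or at the last visit, or says that the table is broken down by treatment.

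The general safety text in the SAP points the other way. Section 2.2 reads "Safety analyses will be conducted using the SS on a treatment-emergent basis", without saying how this applies to examination findings. Section 5.3 adds "Baseline will be defined as the last measurement prior to exposure to investigational product, except otherwise stated". The baseline data exist: at Visit 0, Protocol 12.1.1 has the instructions "Conduct slit lamp examination" and "Conduct dilated fundus examination", each for both eyes.

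In 5.3.5 and 5.3.11 the baseline value appears only in the listings. For the slit lamp, "The listing will include all slit-lamp data from all visits with the following variables", and these variables include the baseline value and the value at the visit. The fundus listing also shows both values.

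**The concern.** An eye with the same minor finding before and after surgery meets the counting rule in both sections. It enters the table as a postoperative abnormality, although neither the lens nor the operation caused it. For the slit lamp there is a second mixture. The examination is done from Day 1-2 onward, so a finding that clears within days and one still present at Visit 4A fall in the same cell.

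SAP 5.2 sets no formal safety hypotheses and makes descriptive assessment the focus of safety. What is at stake is therefore how well two summary tables describe the lenses. A reader comparing the arms wants to know how many eyes acquired a finding and how many still had it at exit. The tables as specified answer neither question.

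**Working it through.** The documents give no slit-lamp or fundus rate, so there is no stated figure to reproduce. The check is a comparison of sections, followed by an illustration on assumed rates.

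**1. How the SAP treats baseline for each examination**

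| SAP section | What is tabulated | Baseline used in the table? |
|---|---|---|
| 5.3.4 IOP | Observed value and change, by visit and treatment; change categories to the last on-treatment assessment and to any visit | Yes |
| 5.3.7 IOL position | Eyes whose position category changed | Yes |
| 5.3.5 Slit lamp | Eyes abnormal at one or more postoperative visits | No; listing only |
| 5.3.11 Dilated fundus | Eyes abnormal at one or more postoperative visits | No; listing only |

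The SAP uses baseline where it says so, and 5.3.5 and 5.3.11 do not say so. A programmer working from those two sections alone would count pre-existing findings. One who applied 2.2 to them would not. The two readings give different tables.

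**2. Is the baseline available for each eye?** Yes. Visit 0 covers both eyes. Visits 1 and 2 examine only the operated eye (Protocol 12.1.3 and 12.1.4), so Visit 0 is the last scheduled preoperative examination for the second eye too.

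**3. Transient against lasting.** Postoperative slit-lamp examinations are at Day 1-2, Day 7-14, Visit 3A and Visit 4A. Scheduled postoperative fundus examinations are only at Visits 3A and 4A. The early-transient mixture is therefore mainly a slit-lamp matter; for the fundus the issue is mainly pre-existing findings. Protocol 13.1 gives weight to persistence: "A persistent AE is an AE that is present at the conclusion of a clinical investigation". The AE tables listed in SAP 5.3.1 cover all AEs, adverse device effects and SAEs, with no split by persistence.

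**4. Illustration (all rates assumed).** Let *p* be the rate of new findings for one parameter. Let *b* be the share of eyes flagged because of a pre-existing finding, equal in both arms and independent of new findings. The table then shows

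1 − (1 − *b*)(1 − *p*) = *b* + (1 − *b*)*p*,

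and the difference between arms is (1 − *b*) times the true difference.

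| Assumed new rates | *b* | Displayed rates | Ratio | Difference (points) |
|---|---|---|---|---|
| 2% v 6% | 0 | 2.0% v 6.0% | 3.0 | 4.0 |
| | 10% | 11.8% v 15.4% | 1.31 | 3.6 |
| | 20% | 21.6% v 24.8% | 1.15 | 3.2 |
| | 30% | 31.4% v 34.2% | 1.09 | 2.8 |
| 5% v 15% | 0 | 5.0% v 15.0% | 3.0 | 10.0 |
| | 5% | 9.75% v 19.25% | 1.97 | 9.5 |
| | 10% | 14.5% v 23.5% | 1.62 | 9.0 |
| | 40% | 43.0% v 49.0% | 1.14 | 6.0 |

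For example, at *b* = 10%: 1 − 0.90 × 0.98 = 0.118 and 1 − 0.90 × 0.94 = 0.154; 0.154 / 0.118 = 1.31.

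The ratio falls quickly as *b* rises and the absolute difference falls slowly. If *b* is near zero, nothing of note is lost. The illustration does not model the transient-against-lasting mixture.

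**The case against.** The strongest reply is that there is no breach. A reader might infer that the SAP deliberately counts pre-existing findings against its own rule. The text does not show that: it nowhere says that such findings are included, and 2.2 can be read as already restricting every safety table. This stands as far as it goes, and the fault is an unreconciled wording. It does not dispose of the point, because the specific sections state a literal count without that restriction and use baseline only in the listings.

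A reader might also infer that new or lasting damage would be hidden. The documents do not support that. The listings show every flagged eye with its baseline value. Conditions present before consent are not AEs (Protocol 13.2), so the AE tables do not carry them. Persistent corneal stromal edema, cystoid macular edema, iritis and raised IOP requiring treatment must be reported as SAEs, which have their own table. What is lost is the contrast between lenses at summary level, since a listing does not give a rate.

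Eligibility narrows the pool of baseline findings. It would be wrong to say that retinal findings are kept out only when the Investigator thinks they could confound outcomes. That qualifier belongs to exclusion criterion 13. Criteria 11 (glaucoma), 12 (degenerative eye disorders) and 14 (optic nerve atrophy) do not carry it, criterion 9 names peripheral retinal pathology as an example, and the note in Protocol 10.1 bars pathology that could reduce visual potential. Minor findings can remain, but a background of 10% to 30% for a single parameter is only an assumption.

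Finally, neither examination is in the protocol's list of safety endpoints (8.4.2). Protocol 15.7 only requires that they be summarized, and no rule demands a Visit 4A column. All of this is correct and bears on severity.

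**Conclusion.** The point holds as a low-severity clarification. SAP 5.3.5 and 5.3.11 give a counting rule that does not fit the treatment-emergent basis of 2.2 or the handling of IOP and IOL position. Followed literally, they produce rates that combine new with pre-existing findings and, for the slit lamp, resolved with lasting ones.

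The size cannot be stated from the documents. It depends on the background rate per parameter, which is not given, and the illustration rests on equal and independent background in the two arms. Individual cases remain visible in the listings and AE/SAE tables, so the evidence supports loss of a summary contrast and not concealment of harm. No hypothesis, alpha level, sample size or primary conclusion depends on these tables.

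**What to change.** In SAP 5.3.5 and 5.3.11, specify that the table shows, by treatment and separately for first and second eyes, the number and percentage of eyes with an abnormality that was absent at the same eye's baseline, or that is worse than baseline where the parameter is graded. Give two columns: any postoperative visit, and Visit 4A. This follows the any-visit and last-assessment layout already used for IOP in 5.3.4. Show eyes without a usable baseline value on their own line. Leave both listings unchanged.

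The cost is SAP wording, a derived variable per parameter and slightly larger tables. No new assessment is needed for the absent-at-baseline rule. The worse-than-baseline part depends on whether the parameters are graded. These documents do not say, because assessment detail is left to the Manual of Procedures; where a parameter is recorded only as normal or abnormal, the absent-at-baseline rule is enough.
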